5. STUDY TREATMENT AND ALLOCATION AND BLINDING

Treatment Allocation

Patients will be assigned in a randomized manner to receive either 1800 mg SC daratumumab in combination with lenalidomide or lenalidomide alone as maintenance therapy and will be stratified prior to randomization by cytogenetic risk (standard risk/unknown versus high risk as defined by presence of del17p, t(4;14), or t[14;16]).

For stratification purposes, if central cytogenetic results are not available (ie, due to technical reasons) or if central cytogenetics assessment was not conducted due to availability of local results, local cytogenetic results may be used with the approval of the medical monitor. If central and local cytogenetic results are not available, the patient will be assumed to have normal/standard cytogenetics. The investigator will screen patients for enrollment and if eligible, randomize each patient using an interactive web response system (IWRS). Each patient will be assigned a unique patient number. For enrollment and treatment randomization, MRD status will be assessed using the Adaptive Biotechnologies' NGS-based MRD assay, if available.

Blinding

As this is an open study, blinding procedures are not applicable.

6. DOSAGE AND ADMINISTRATION

6.1. Daratumumab and Lenalidomide Dosing and Supply

Maintenance treatment regimens in this study comprise of SC daratumumab in combination with lenalidomide or lenalidomide alone as follows (each cycle will be 28 days in duration with a total of 36 cycles, the planned maximum duration of treatment; every effort should be made to keep patients on the planned dosing schedule):

Daratumumab 1800 mg administered by SC injection:

- Weekly during C1 and C2,
- Every 2 weeks during C3 to C6, and
- Every 4 weeks from C7 onwards until confirmed PD, unacceptable toxicity, or until end of study treatment.

Lenalidomide 10 mg PO:

- D1 to D28 (continuously) of each 28-day cycle until confirmed PD, unacceptable toxicity, or until end of study treatment. If a patient experiences toxicity to lenalidomide, dose and/or schedule may be modified per institutional standard.
- After 3 cycles of maintenance therapy, if well tolerated, the lenalidomide dose may be increased to 15 mg daily, at the discretion of the investigator.

The start of each cycle may occur ± 3 days of the scheduled day to accommodate the schedule of the site or patient. Day 1 of subsequent cycles should be adjusted accordingly to maintain the intended cycle duration. Any delays ≥ 4 days of the scheduled day will need to be discussed with the sponsor.

Daratumumab will be prepared and administered on site, on an out-patient basis, as described in Section 6.2. Guidelines for the prevention and management of daratumumab administration reactions are also described in this section. For further instructions on dose delays due to daratumumab toxicity, please refer to Section 6.3.2.

Lenalidomide will be obtained and administered in accordance with the requirements of the REVLIMID REMS[®] program or the lenalidomide Global Pregnancy Prevention Plan (when lenalidomide is supplied centrally and no local lenalidomide REMS program exists) in Attachment 3. Patients will self-administer lenalidomide and be instructed as follows:

- To swallow capsules whole with water once a day; preferably at the same time each day. Lenalidomide may be taken with or without food.
- To **not** open, break, or chew capsules.
- To **not** handle capsules any more than needed. If a broken lenalidomide capsule or the medicine inside the capsule is touched, the patient should wash the area of his/her body with soap and water.
- If a dose is missed and it has been less than 12 hours since the prior dose, the patient should take lenalidomide as soon as remembered. If it has been more than 12 hours, he/she should skip the missed dose. Two doses should not be taken at the same time.
- How to store lenalidomide for at-home use.
- How to document lenalidomide intake in the diary provided by the site.

Guidelines for dose adjustment of lenalidomide in the event of toxicity or for renal impairment are provided in Section 6.3.3, Lenalidomide.

For patients receiving both daratumumab and lenalidomide, it is recommended that lenalidomide be taken either prior to or at the same time (preferred) as the daratumumab pre-administration medications that are to be taken within 1 to 3 hours prior to daratumumab administration (see Section 6.2.2.1).

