6.3.2.2. Daratumumab-related Toxicity Management

Refer to Section 6.2.3 for details on management of daratumumab injection-related reactions.

If any of the following criteria are met and the toxicity is more than expected for lenalidomide or underlying multiple myeloma, daratumumab injection must be held to allow for recovery from toxicity. If attribution is unclear, then daratumumab should be held until recovery from toxicity as noted below.

The criteria for a dose delay are:

- Grade 4 hematologic toxicity, except for Grade 4 lymphopenia
- Grade 3 thrombocytopenia with bleeding
- Febrile neutropenia
- Neutropenia with infection, of any grade
- Grade 3 or higher non-hematologic toxicities with the following exceptions:
 - Grade 3 nausea that responds to antiemetic treatment within 7 days
 - Grade 3 vomiting that responds to antiemetic treatment within 7 days
 - Grade 3 diarrhea that responds to antidiarrheal treatment within 7 days
 - Grade 3 fatigue that was present at baseline or that lasts for <7 days after the last administration of daratumumab
 - Grade 3 asthenia that was present at baseline or that lasts for <7 days after the last administration of daratumumab

Administration of daratumumab may be restarted upon recovery from toxicity to Grade 2 or baseline, with the exception that Grade 2 laryngeal edema or Grade 2 bronchospasm must be fully recovered. Other than on Day 1 of a cycle, if any "within-cycle" daratumumab administration does

not commence within the prespecified window of the scheduled administration date (Table 4), then the dose will be considered a missed dose. Administration may resume at the next planned dosing date.

Daratumumab Dosing Frequency	Dose Missed	Dosing Resumption
Weekly	>3 days	Next planned weekly dosing date
Every 2 weeks	>7 days	Next planned every-2-weeks dosing date
Every 4 weeks	>21 days	Next planned every-4-weeks dosing date

 Table 4:
 Daratumumab-related Toxicity Management

A missed dose will not be made up. Delay of Day 1 drug dosing in any given cycle should not result in a skipped dose but should lead to a delay of the entire cycle instead. A minimum of 4 days between daratumumab doses must be observed.

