6.3.3. Lenalidomide

The lenalidomide dose may be reduced, or the treatment schedule may be modified for the management of study drug-related toxicities. For example, if a patient develops a drug-related toxicity that requires a dose or schedule modification while receiving lenalidomide 10 mg on D1 to D28 (continuously) of each 28-day cycle, the dose of lenalidomide may be reduced to ≤ 10 mg on D1 to D28 of each 28-day cycle. Alternatively, the dose and treatment schedule may be modified to ≤ 10 mg on D1 to D21 of each 28-day cycle, per institutional standard.

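### The lenalidomide missed-dose rule counts 12 hours from the prior dose, so on a once-daily schedule every missed dose is skipped

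*Protocol*

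**What the plan says.** Protocol Section 6.1 sets lenalidomide at 10 mg by mouth on "D1 to D28 (continuously) of each 28-day cycle until confirmed PD, unacceptable toxicity, or until end of study treatment". The investigator may raise it to 15 mg daily after three cycles. Patients give themselves the drug and are instructed "To swallow capsules whole with water once a day; preferably at the same time each day".

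The missed-dose bullet in the same section has two branches. The first reads "If a dose is missed and it has been less than 12 hours since the prior dose, the patient should take lenalidomide" as soon as they remember. The second reads "If it has been more than 12 hours, he/she should skip the missed dose". A closing sentence bars taking two doses at once. Both branches run on one clock, which starts at the prior dose.

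Section 6.1 also asks, for both regimens, that "every effort should be made to keep patients on the planned dosing schedule".

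For daratumumab, Section 6.3.2.2 starts the clock elsewhere. A within-cycle injection that does "not commence within the prespecified window of the scheduled administration date (Table 4), then the dose will be considered a missed dose", and that section states outright that missed daratumumab doses are not made up.

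**The concern.** A rule with two branches is meant to separate capsules remembered soon enough to take from those remembered too late. For a drug taken every 24 hours, a 12-hour limit does this only if it is counted from the time the missed capsule was due. Counted from the prior capsule, the limit has passed 12 hours before the next capsule falls due, so the rule always returns the same answer.

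This is a working instruction for a self-administered drug. Lenalidomide is given in both arms, is the whole regimen in the control arm, and runs for up to 36 cycles. A patient who follows the text as written and remembers a missed capsule a few hours late loses that day's dose. That sits poorly with the same section's request to hold to the planned schedule. What is at stake is avoidable loss of exposure and inconsistent instructions between sites that read the bullet literally and sites that guess its intent.

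**Working it through.** **Inputs.** All are from Protocol Section 6.1: one dose every 24 hours; no rest days within the 28-day cycle; a 12-hour limit counted from the prior dose; 10 mg per dose. The plan gives no figure of its own on this point to reproduce.

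**Step 1: prior dose on time.** Let x ≥ 0 be the hours after the usual time at which the missed dose is remembered.

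- Hours since the prior dose = 24 + x.
- The take branch needs 24 + x < 12, that is x < −12.
- No missed dose can meet this. If the prior dose was itself skipped, the elapsed time is longer still.

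| Remembered late by (x) | Hours since prior dose (24 + x) | Rule as written | Counted from due time | Hours to next due dose (24 − x) |
|---|---|---|---|---|
| 1 h | 25 | skip | take | 23 |
| 6 h | 30 | skip | take | 18 |
| 11 h | 35 | skip | take | 13 |
| 13 h | 37 | skip | skip | 11 |

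The two rules differ only for doses remembered 0 to 12 hours late, which is 24 to 36 hours after an on-time prior dose. Beyond 12 hours late, both say skip.

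**Step 2: prior dose late.** Suppose the prior dose was taken d hours after its usual time.

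- Hours since the prior dose = 24 + x − d.
- The take branch needs d > 12 + x. For x = 0, d > 12; for x = 1, d > 13.

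So the branch opens only when the prior capsule was more than 12 hours late, which the same rule would normally have sent to skip. It would then have the patient take another dose within 12 hours of the last one, which is the reverse of its purpose. The ban on taking two doses at once covers only simultaneous doses.

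**Step 3: dose lost.** Planned dose per cycle = 28 × 10 mg = 280 mg.

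- One affected dose: 10/280 = 3.6%.
- Two: 20/280 = 7.1%.
- Three: 30/280 = 10.7%.

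The fraction is 1/28 per dose at 15 mg as well. The number of affected doses per cycle is an assumption, and with none the loss is 0%.

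**Step 4: whether another section corrects it.** Section 6.3.3 concerns toxicity only: "The lenalidomide dose may be reduced, or the treatment schedule may be modified for the management of study drug-related toxicities". Section 6.4.2 covers overdose, Section 7 covers diary recording, and Attachment 3 covers pregnancy prevention. None restates or corrects the missed-dose rule.

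**The case against.** The strongest objection is that the protocol never defines a missed lenalidomide dose. Taking it at the same time each day is only a preference, so a capsule taken two hours late still meets the once-daily requirement and might count as late, not missed. On that reading the bullet is not triggered and little or nothing is lost. It is fair that the real loss cannot be shown. But if same-day capsules are never missed, the take branch still has nothing to act on, so this reading does not make the rule work.

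A second reading takes the prior dose to be the scheduled dose just missed. Both branches then work, and this is very likely what was meant. It is not what the sentence says, and a patient instruction should not depend on it.

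Three further points stand:

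- The literal rule errs towards skipping, so routine double-dosing is not a risk.
- Intake is recorded in a diary, and SAP Section 4.3 summarises skipped doses with reasons, so some trace would remain. The relative dose intensity in that section would not show it, because its planned dose counts only administered doses. Dose intensity per cycle could.
- Patient-facing text is not in these documents, so what patients were actually told is unknown.

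The daratumumab comparison is limited too. Those are clinic injections with windows of days, so it shows a sensible starting point for the clock and not a template. It also shows that where the sponsor wants no make-up doses, the protocol says so.

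**Conclusion.** The rule is wrong as written. On a regular once-daily schedule its take branch cannot apply, and every missed lenalidomide dose is skipped. The one exception needs a prior capsule more than 12 hours late, and there the instruction works backwards.

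The doses affected are missed capsules remembered within 12 hours of the usual time, each worth 3.6% of that cycle's planned dose. Under an assumed one to three such doses in a cycle, that cycle loses 3.6% to 10.7%; a cycle with none loses nothing. No missed-dose rate is given, so expected loss over the trial cannot be stated. The size also assumes that patients and sites follow the text literally and treat a late capsule as missed.

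The rule is identical in both arms. Nothing here affects the sample size, the type I error or the primary analysis. The severity is minor, and confidence in the reading of the text is high.

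**What to change.** Start the 12-hour clock at the time the missed capsule was due. In substance: a capsule remembered less than 12 hours after its due time is taken on remembering; one remembered later than that is left out, and the next is taken at the usual time. This leaves at least 12 hours before the next scheduled dose. Keep the sentence barring two doses at once. The revision should also say which branch applies at exactly 12 hours, which the present wording leaves open.

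The sponsor's medical team should check the new wording against the lenalidomide prescribing information and align any patient-facing instructions that repeat the old one.

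The cost is one protocol bullet and any matching patient text. Visits, sample size and analysis do not change.

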6.2. Daratumumab

6.2.1. Preparation and Administration

Detailed instructions for preparation, administration, and storage of daratumumab will be supplied in study reference materials; please refer to the Commercial Prescribing Instructions for drug preparation and administration. An overview of this information is provided below.

In the SC daratumumab group, daratumumab will be provided as a fixed-dosed (1800 mg), combination drug product containing rHuPH20 drug substance (2000 U/mL) and daratumumab

drug substance (120 mg/mL) in a single vial. Manuals with detailed descriptions for preparation and administration of daratumumab will be supplied to each pharmacy and site.

Daratumumab (1800 mg) will be administered by SC injection by manual push over approximately 3 to 5 minutes in the abdominal SC tissues in left/right locations, alternating between individual doses. The volume of the SC solution will be 15 mL for the 1800 mg dose. Refer to the Site Investigational Product Procedures Manual (SIPPM) for additional guidance on SC administration of daratumumab. All patients will be observed for at least 6 hours after the end of the SC injection during Cycle 1 Day 1 and, if deemed necessary by the investigator, after subsequent injections. Reasons for continued observation on subsequent daratumumab injections may include but are not limited to the following: patients with a higher risk of respiratory complications (eg, patients with mild asthma or patients with COPD who have an FEV1 <80% at screening or developed FEV1 <80% during the study without any medical history), patients with IRR with first injection of study drug, patient with a decreased condition on day of dosing compared to prior dosing day. The dose of daratumumab will remain constant throughout the study.

Cycles	Schedule
Cycles 1 to 2	weekly (total of 8 doses)
Cycles 3 to 6 ^a	every two weeks (total of 8 doses)
Cycle 7 onwards until confirmed disease progression, unacceptable toxicity, or end of study treatment ^b	every four weeks
^a First dose of the every-2-week dosing schedule is gi ^b First dose of the every-4-week dosing schedule is gi	ven at Week 9 ven at Week 25

 Table 2:
 Daratumumab Dosing Schedule

All daratumumab administrations will be in an outpatient setting. Patients will receive preinjection medications and post-injection medications as outlined in Section 6.2.2.1 and Section 6.2.2.2, respectively.

As noted in the Time and Event Schedule, vital signs should be monitored extensively on Cycle 1 Day 1 before, and after the first administration of daratumumab. For all other administrations, vital signs should be measured before the start of injection and at the end of the injection as shown in the Time and Events Schedule – Part 1. If the patient experiences any significant medical event, then the investigator should assess whether the patient should stay overnight for observation. If the patient has not experienced a significant medical event but is hospitalized overnight only for observation, then the hospitalization should not be reported as a SAE. Patients will be provided with a diary to record intake of pre- and post-administration medications taken while off-site; sites will use information to complete exposure information in the eCRF. If an IRR develops, then the injection should be temporarily interrupted or slowed down. In the event of a life-threatening IRR (which may include pulmonary or cardiac events) or anaphylactic reaction, SC daratumumab should be discontinued, and no additional SC daratumumab should be administered to the patient. See Section 6.2.3 for instructions on the management of IRR and local ISRs.

Every effort should be made to keep patients on the planned dosing schedule; however, doses given ± 3 days of the scheduled dose are permitted. Any delays ≥ 4 days of the scheduled day will need to be discussed with the sponsor.

6.2.2. Daratumumab Pre- and Post-administration Medications and Patient Observation

The following subsections provide information on medications to be administered prior to and after daratumumab administration to prevent or ameliorate potential administration reactions. Instructions for patient observation following daratumumab administration are also described.

If an IRR develops, then the injection should be temporarily interrupted or slowed down. In the event of a life-threatening IRR (which may include pulmonary or cardiac events) or anaphylactic reaction, SC daratumumab should be discontinued and no additional SC daratumumab should be administered to the patient. For management of administration reactions related to daratumumab refer to Section 6.2.3, and for instructions on dose delays due to other toxicities assessed as related to daratumumab or lenalidomide, refer to Section 6.3.

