6.2.3.2. Daratumumab Injection-related Reactions

Patients should be carefully observed during daratumumab administration. Trained study staff at the clinic should be prepared to intervene in case of any injection-related reactions, and resources necessary for resuscitation (eg, agents such as epinephrine and aerosolized bronchodilator, also medical equipment such as oxygen tanks, tracheostomy equipment, and a defibrillator) must be available at the bedside. Attention to staffing should be considered when multiple patients will be dosed at the same time.

Patients who experience AEs during daratumumab administration must be treated for their symptoms:

- Treatment with acetaminophen, antihistamine, or corticosteroids, may be administered as needed.
- IV saline may be indicated.
- For bronchospasm, urticaria, or dyspnea, patients may require antihistamines, oxygen, corticosteroids, or bronchodilators.
- For hypotension, patients may require vasopressors.

In the event of a life-threatening reaction (which may include pulmonary or cardiac events) or anaphylactic reaction, daratumumab-SC should be discontinued, and no additional daratumumab should be administered to the patient; and the patient must be permanently withdrawn from daratumumab treatment.

6.2.3.2.1. Injection-related Reactions of Grade 1 or Grade 2

If the investigator assesses a Grade 1-2 IRR to be related to administration of study intervention, then the daratumumab SC administration should be interrupted. When the patient's condition is stable, daratumumab SC administration may be restarted at the investigator's discretion. Refer to the SIPPM for further details regarding continuation of daratumumab SC administration.

If the patient experiences a Grade 2 or higher event of laryngeal edema or a Grade 2 or higher event of bronchospasm that does not respond to systemic therapy and does not resolve within 6 hours from onset, then the patient must be permanently withdrawn from daratumumab SC treatment.

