6.2.3.2.2. Injection-related Reactions of Grade 3 or Higher

For injection-related reactions (other than laryngeal edema or bronchospasm) that are Grade 3, the daratumumab SC administration must be stopped, and the patient must be observed carefully until resolution of the adverse event or until the intensity of the event decreases to Grade 1, at which point the daratumumab SC administration may be restarted at the investigator's discretion. Refer to the SIPPM for further details regarding continuation of daratumumab SC administration.

If the intensity of the event returns to Grade 3 after restart of the daratumumab SC administration, then the patient must be permanently discontinued from daratumumab SC treatment.

For injection-related AEs that are Grade 4, the daratumumab SC administration must be stopped, and the patient permanently discontinued from daratumumab SC treatment.

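### Sections 6.2.1 and 6.2.2 let an injection be slowed for any injection-related reaction that is not life-threatening or anaphylactic; this clashes with the Grade 3 stop rule, and for Grade 3 bronchospasm it is the only text on the injection in progress

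*Protocol*

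**What the plan says.** **General instruction.** Protocol 6.2.1 and 6.2.2 carry the same sentence: "If an IRR develops, then the injection should be temporarily interrupted or slowed down". Each follows it with one exception: for a life-threatening or anaphylactic reaction, daratumumab is discontinued. Section 6.2.1 introduces its content with "An overview of this information is provided below" and later adds "See Section 6.2.3 for instructions on the management of IRR and local ISRs". Section 6.2.2 has a similar pointer: "For management of administration reactions related to daratumumab refer to Section 6.2.3".

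**Graded instructions in 6.2.3.2.**
- Grade 1-2: "If the investigator assesses a Grade 1-2 IRR to be related to administration of study intervention, then the daratumumab SC administration should be interrupted".
- Grade 3: "For injection-related reactions (other than laryngeal edema or bronchospasm) that are Grade 3, the daratumumab SC administration must be stopped". Once the event "decreases to Grade 1, at which point the daratumumab SC administration may be restarted" at the investigator's discretion.
- Grade 4: "For injection-related AEs that are Grade 4, the daratumumab SC administration must be stopped", and daratumumab is permanently discontinued.

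**Airway events.** Section 6.2.3.2.1 requires permanent withdrawal for laryngeal edema or bronchospasm of Grade 2 or higher, with a qualifier about failing to respond to systemic treatment and persisting past 6 hours. The grammar leaves open whether that qualifier covers both events or bronchospasm alone. Section 6.2.3.2.3 requires permanent discontinuation if such an event recurs. Sections 6.3.1 and 6.3.2.2 require full recovery from either event at Grade 2 before daratumumab resumes.

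**The concern.** Staff giving the injection need one answer to one question: when a reaction starts, do they slow, pause or stop? The general sentence offers slowing, and the graded section never does. At Grade 3 the difference is between an optional reduction in speed and a mandatory stop.

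The second problem lies inside the graded section. The Grade 3 stop rule sets laryngeal edema and bronchospasm aside, and no other sentence says to stop the injection when one of them occurs at Grade 3. The protocol treats these airway events more strictly than other reactions elsewhere, since its withdrawal and recurrence rules for them begin at Grade 2. It would be odd for slowing to stay open for them at Grade 3. What is at stake is the safety of individual patients in the daratumumab arm during a manual push of about 3 to 5 minutes. The statistical design is not involved.

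**Working it through.** No arithmetic applies. The check sets the instructions for the injection in progress side by side, by grade. Grade meanings come from Protocol 12.1.3, where Grade 3 is not immediately life-threatening and Grade 4 is life-threatening.

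| Reaction during the push | General sentence (6.2.1, 6.2.2) | Graded rule (6.2.3.2) | Result |
|---|---|---|---|
| Grade 1-2, judged related | interrupt or slow (should) | interrupt (should) | slowing is looser than the graded rule |
| Grade 1-2, not judged related | interrupt or slow (should) | silent | no contradiction |
| Grade 3, not airway | interrupt or slow (should) | stop (must) | slowing directly conflicts |
| Grade 3 bronchospasm | interrupt or slow (should) | excluded from the stop rule | general sentence stands alone |
| Grade 3 laryngeal edema | interrupt or slow (should) | excluded from the stop rule | depends on the 6-hour clause |
| Grade 4 | exception applies: discontinue | stop (must) and discontinue | no conflict |

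**Grade 3 bronchospasm.** The other text that reaches this event answers different questions:
1. Section 6.2.3.2 requires symptomatic treatment of events during administration and names bronchospasm, but does not say what happens to the push.
2. Section 6.2.3.2.1 decides on permanent withdrawal, which turns on what has happened by 6 hours.
3. Section 6.2.3.2.3 decides on permanent discontinuation if the event recurs with a later dose.
4. Section 6.3.2.2 holds daratumumab for Grade 3 or higher non-hematologic toxicity. It is a dose-delay rule and sends injection-related reactions back to 6.2.3.

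None of these says to stop the injection. The Grade 1-2 and Grade 4 rules do not exclude airway events, so Grade 3 is the one grade from 1 to 4 with no graded rule for the push.

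**Grade 3 laryngeal edema.** If the 6-hour qualifier belongs to bronchospasm alone, laryngeal edema of Grade 2 or higher already means permanent withdrawal, and the gap closes. If it belongs to both events, the gap is the same as for bronchospasm.

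**Frequency.** Protocol 3.2.2.2 gives two Grade 3 figures for subcutaneous daratumumab: a 1.5% incidence in the randomized comparison with intravenous dosing, and two hypertension events among 25 patients given 1800 mg in the phase 1b study. Neither isolates airway events or says how many reactions began during the push, so no patient count follows from them.

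**The case against.** The strongest reply is that 6.2.3 is the designated management section. Both general sections point to it close to the disputed sentence, 6.2.1 presents its text as an overview, and a specific *must* outranks a general *should*. That largely answers the mismatch for non-airway Grade 3 reactions, and it is why the practical effect is small. It does not answer Grade 3 bronchospasm, because a reader who follows the pointer finds that event carved out of the stop rule.

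A second reply is that the general sentence itself covers Grade 3 bronchospasm and offers interruption, so deleting the slowing option would close most of the gap. This is fair. The deletion is the main fix, and the added stop sentence brings the airway events up to the level of other Grade 3 reactions.

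A third is that the carve-out may be meant to keep airway events off the restart-at-Grade-1 path. That is plausible, but the text does not say so, and the same words also remove the stop instruction.

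Finally, 6.2.1 and 6.2.3.2 refer administration detail to the Site Investigational Product Procedures Manual, and 6.2.1 also cites the commercial prescribing instructions. Neither is among the documents. The point is therefore about protocol wording, and a reader should not infer that site instructions are deficient.

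**Conclusion.** The point holds in limited form. Slowing conflicts directly with the mandatory stop for non-airway Grade 3 reactions and is looser than the advice for related Grade 1-2 reactions. For Grade 3 bronchospasm, the sentence that permits slowing is the only text on the injection in progress. For Grade 3 laryngeal edema, this is so only if the 6-hour clause covers it.

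Three stronger readings are tempting but unsupported:
- A reader might infer that slowing breaches the rule at every grade. It does not at Grade 4, which falls under the discontinuation exception. At Grades 1-2 both texts say *should*, and the graded rule applies only to reactions judged related.
- A reader might infer that Grade 3 airway events have no instructions at all. They have rules on treatment, withdrawal, recurrence and dose holding; only an express stop is missing.
- A reader might infer that the protocol forbids restarting a dose stopped for such an event. It does not say so.

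The conclusion rests on the protocol text alone. It is a minor, low-frequency safety wording correction whose frequency cannot be quantified from the documents. Endpoint, power and analysis are unaffected.

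**What to change.** At the next protocol amendment:
1. In 6.2.1 and 6.2.2, delete the words *or slowed down*.
2. In 6.2.3.2.2, add: *For Grade 3 laryngeal edema or bronchospasm, the injection must be stopped; withdrawal follows Section 6.2.3.2.1.*
3. In 6.2.3.2.1, state whether the 6-hour clause applies to laryngeal edema as well as bronchospasm.

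Whether a dose stopped for a Grade 3 airway event may be restarted is a clinical decision for the sponsor; if one is made, it should be written next to the new sentence. The procedures manual should be checked for agreement.

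The cost is three words removed in two places, one sentence added, one clause clarified and one manual check. Data collection, endpoints and sample size do not change.
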